Which are applicable to your study: Drug Device Radiolabeled drug/compound

Off Label and Investigational Use of Drugs

Enter the information for all drugs to be used in this study:

Name of the drug	N/A
Manufacturer and other Information	N/A
Approval Status (select one)	No IND is required – N/A
IND #	N/A
Who holds the IND (i.e., IND Sponsor). If other than PI/CU Investigator, type name of holder.	N/A
Which applies:	FDA has determined the IND is not required (provide correspondence) FDA conditions are met (see “Rules”) – Explain https://www.fda.gov/drugs/investigational-new-drug-ind-application/ind-application-procedures-investigators-responsibilities N/A

Off Label and Investigational Use of Devices

Enter the information for all devices to be used in this study:

Name of the device	
Manufacturer and other Information	
Approval Status (select one)	IDE application is pending IDE is approved No IDE is required
IDE #	
Who holds the IDE (i.e., IDE Sponsor). If other than PI/CU Investigator, type name of holder.	
Is the device marketed?	
Which applies:	FDA has determined that IDE is not required FDA conditions are met (see “Rules”) – Explain https://www.fda.gov/medical-devices/investigational-device-exemption-ide/ide-application Device is “Non-significant risk” – Explain

Off Label and Investigational Use of Radiolabeled Drugs / Compounds

Enter the information for all radiolabeled drug/compounds to be used in this study:

Name of the radiolabeled drug/compound	
Manufacturer and other Information	
Approval Status (select one)	IND application is pending IND is approved RDRC approval is pending RDRC is approved No FDA/RDRC approval is required - Explain
IND #	
Who holds the IND (i.e., IND Sponsor). If other than PI/CU Investigator, type name of holder.	

Research Related Delay to Treatment

Research involving participants who are in need of treatment invariably involves delay to care, and this delay is associated with risk. Scheduling of procedures must be carefully organized to minimize delay. Other delay

Protocol Summary Form

must involve only that minimally necessary to accomplish the aims of the research while respecting subject well-being and safety. Describe the delay, by virtue of research participation in this study, before a participant can receive treatment of known efficacy or standard care routinely offered in the community.

Most transitions from MCI to AD will occur by 3 years of follow-up. We chose 18 months to decrease dropout that can occur in a very long controlled trial. There will be no treatment provided at the end of the study. Once a subject completes the final study visit, inclusive of the endpoint MRI, the subject will be finished with protocol procedures and given an appropriate clinical referral.

Clinical Treatment Alternatives

Describe what other treatment or assessment options are available to subjects who do not participate in research.

The patient does not have to join this study to receive treatment for memory loss. If the patient decides not to participate, the patient may review treatment options with their doctor.

Risks/Discomforts/Inconveniences

"Risk" is a broad term used to convey the potential for harm, burden, and inconvenience related to research participation. Use this section to provide a comprehensive description of foreseeable physical, psychological, social, interpersonal, and economic risks introduced by the research. Include the source of the information. Consider both the probability and magnitude of harm and its impact. Describe the foreseeable harms associated with the research (untoward effects of a medication) and those related to delay to individualized treatment. Include data from the literature, and local data, if available, on risk rates and subject experiences with research procedures. Describe procedures in place to minimize risk. In general, please create a numbered list of risks/categories of risk, and in general put the list in the order of significance or level of risk, the most significant risks should be listed first.

Risks that could be encountered during the study period:

MRI Scan:

The MRI, conducted at baseline and week 78, does not pose undue risk.

MRI involves lying on a bed which slides into a large cylindrical magnet. Radiowaves are used to obtain images from the internal parts of the subject's body. Before beginning the imaging procedure, we will ascertain that the subject does not have a pacemaker or any metallic implants (other than tooth fillings), and the subject will be asked to remove any metal or magnetized objects (such as keys, chains, hairpins, or credit cards). The subject will be asked to lie flat on their back in the MRI scanner for approximately 45 minutes. The subject will be asked to remain as still as possible. The subject will not feel anything, but will hear a banging noise. If claustrophobia unexpectedly develops during the procedure, we will stop the MRI scan and consider repeating it at a later date.

Protocol Summary Form

Neuropsychological Assessment:

During neuropsychological testing, some subjects may find some questions upsetting. The tester will discuss the situation with the patient and will allow for an expanded break between tests when feasible. If the patient still chooses not to proceed with testing, the patient's choice will be respected.

Remote Assessments:

Select subject neuropsychological testing and informant interviews may be administered remotely throughout stage I re-opening, as described in previous section of PSF. MRI and majority of subject neuropsychological testing must be completed in person, on site.

With completion of remote assessments also comes the risk for loss of confidentiality. Remote assessments will be administered exclusively through the HIPAA compliant phone calls at a time agreed upon by both the subject and/or informant, and member of the study team. The individual completing the remote assessments will do so by completing tests and/or interviews verbally, and recording replies on paper CRF, for later storage in the subject chart.

Travel for Research Purposes:

During Stage I re-opening: research participants will only come on-site if absolutely necessary for completion of study assessments and procedures. Any participant coming to NYSPI or Cornell facilities for conduct of study assessments and procedures will be at increased risk of contracting COVID-19 en route, but the Principal Investigator and study team will take all precautions necessary to ensure that risk remains minimal, including paying for the transport of participants to site via car service or ride share (utilizing services such as Uber or Lyft). Research Coordinator will remind participants to wear mask and practice frequent hand hygiene while in transport to study visit, during the 24 hour pre-visit reminder call.

In Person Visits and Procedures:

While on site during stage I re-opening, all guidelines and procedures specific to COVID-19 risk reduction (described in "Study Procedures" section, and uploaded as stand alone documents in the "Uploads" section of PRISM) will be implemented by study team and adhered to by participants, in order to reduce the spread of COVID-19 to staff and participants at NYSPI/CUMC facilities. Any staff or participant unwilling to abide by these guidelines will not be permitted to participate in, or complete work at the study visit.

Apolipoprotein E genotyping. In the informed consent form, we will state (1) the presence of specific subtypes of apolipoprotein may be associated with an increased risk of memory disorders, (2) the results will be kept strictly confidential and not released to the subject or to other parties. This approach, required by our IRB for all apolipoprotein genotyping studies, follows from the current ambiguities for clinical application of apolipoprotein E genotyping. Further, given that this involves genotyping, as per our NYSPI IRB requirements, a Certificate of Confidentiality will be obtained from NIA, as we have done in other studies

Procedures for Minimizing Risks:

Protocol Summary Form

There are three areas in which safeguards to protect subjects from undue risk require discussion. These include the procedures used to obtain informed consent, the procedures used to ensure confidentiality of subjects' responses and findings on tests, and the procedures used to minimize possible risks associated with the research procedures.

Informed Consent. Informed consent is obtained and documented with a signed consent statement giving full information about the study. In the consent form and in discussion with an investigator, subjects are advised fully of the procedures to be used, the amount of time required of them, the fact that this is a longitudinal treatment study with repeated assessment at specified time points, the possible risks and benefits of the procedures and the treatment conditions, their right to refuse participation in the study without prejudice, their right to terminate participation at any moment without prejudice, and the name and telephone number of the Principal Investigator.

Capacity to Consent. Based on IRB requirements, patients will be recruited by a study physician who signs the consent form in addition to the patient. As described earlier, for patients who lack the capacity to consent but retain the capacity to appoint a surrogate, we will follow the procedures required by the NYSPI IRB (based on New York State OMH regulations) regarding assessment of capacity to consent.

Research Procedures. We have described above the potential risks of the research procedures and the safeguards that will be used to minimize risks. These include termination of subjects from research participation if it is believed that such participation endangers their welfare. Monitoring procedures are used to evaluate potential side effects of research procedures. The protocol stipulates an extensive medical, neurological, and psychiatric evaluation of all subjects as a condition for research participation.

Methods to Protect Confidentiality

Describe the data management plan and the methods you will employ to protect subject privacy and the confidentiality of research data. The section should detail how information will be collected, recorded, coded, stored, transmitted, and as applicable, shared with other investigators so as to minimize risks related to breach of confidentiality. Confirm that identifiers are removed, to the extent possible, from research data, and explain if there are links between subject identity and research data, or if the data are anonymous. Also, indicate where the data are stored, who is responsible for data safekeeping, and who has access to subject identity and codes, if any, which cross-link research data and subject identity. Confirm that identifiable data are not collected, stored, or transmitted by mail, fax, on removable drives, laptops, or via the internet without proper protections, e.g. encryption.

In the informed consent form, subjects are told that the information they provide and all findings will be kept strictly confidential, with access limited to the research staff with the possible exception of State or Federal regulatory personnel for audits. All records are kept in locked files. Each subject is given a code number for database purposes, and the patient's name does not reside in the database. Computer files will be stored in a database that is password protected and behind an institute and department firewall. No one but the project staff has access to the master list linking subjects' names to code numbers, and all information obtained is coded.

The master list is kept under strict lock and key. The research data on specific measures are released to the patients, and this is specified in the consent form.

Will the study be conducted under a certificate of confidentiality?

- Yes, we will apply for the Certificate of Confidentiality
- Yes, we have already received a Certificate of Confidentiality
- No

Direct Benefits to Subjects

Describe only benefits to individual subjects that are likely to accrue during the study itself. Do not include subject compensation or treatment to be provided at the end of the study, as these do not figure into the IRB's risk/benefit considerations. Do not describe diagnostic and evaluation components unless subjects receive clinical feedback. Do not describe the anticipated scientific benefits of the research. Some studies offer no direct benefit to subjects.

Participants may or may not benefit from study participation.

Compensation and/or Reimbursement

If compensation or reimbursement for expenses will be offered to subjects, please describe and indicate total amount and schedule of payment(s). If transportation is reimbursed, state if receipts are necessary for reimbursement. Include justification for compensation amounts and indicate if there are bonus payments.

Subjects will receive \$50 per MRI scan (baseline and 78 weeks) and \$25 at each of the major time points: baseline, 12 weeks, 20 weeks, 32 weeks, 52 weeks, 78 weeks. Participants will be compensated \$1 per completed at-home online training session for both training groups. This will be an extra \$72 dollars maximum per participant, if he/she completes all required sessions. Therefore, subjects will receive a total of \$322 for their participation in the study over the course of 18 months.

Data Management Plan

All federally funded, more than minimal risk studies are required to include a Data Management Plan. The required elements of the Data Management Plan include: identification of the database platform (e.g., REDCap) and inclusion of an attestation that it is Part 11 compliant, identification of a qualified staff member who designs and maintains the database, design and implementation of data system training for all Principal Investigators & research coordinators & all protocol staff, and significant changes to the data management plan will be submitted as protocol amendments in PRISM. More information can be found on the IRB website at <https://irb.nyspi.org/forms> regarding this plan and should be reviewed prior to submission.

Protocol Summary Form

The data collected in this study will be entered and monitored by the Database Management Unit at NYSPI. This unit is headed by [name], whose unit has 2000 square feet of office space, and can easily accommodate the data management activities in this proposal.

References

Please limit references, preferably no more than twenty.

2. Petersen RC. Mild cognitive impairment as a diagnostic entity. *J Intern Med*. 2004;256:183-194.

Statistical Analysis Plan for "Home-Based Computerized Cognitive Training for Mild Cognitive Impairment: 78-week randomized blinded trial of crossword puzzles versus games"

#### 1. Introduction.

The aim of the study was to evaluate the efficacy of computerized cognitive training (suite of videogames, denoted as "Games") as compared to computerized crossword puzzle training (denoted as "Crosswords") in the two-site, 78-week, COG-IT randomized clinical trial for study participants with mild cognitive impairment (MCI). This statistical analysis plan provides more detailed descriptions of the statistical analyses reported in the paper.

# 2. Study Design

One hundred and seven participants aged 55-95 years with clinical diagnosis of MCI were randomized to Games or Crosswords at 1:1 ratio. The randomization was stratified by site (Columbia or Duke), MCI type (early or late MCI), and age (70 years and below or 71 and above). Block randomization of random size (2,4) was used to prevent clinicians from guessing what the next participant's treatment might be. Participants were evaluated at five scheduled visits (Weeks 0, 12, 32, 52, and 78) and research staff conducted three scheduled phone calls (Weeks 20, 42, and 64). Home-based computerized training for Games or Crosswords comprised four 30-minute training sessions weekly for 12 weeks. The six booster sessions each consisted of four 30-minute sessions. At weeks 32, 52, and 78, participants completed three booster sessions at home and the fourth in-clinic. At weeks 20, 42, and 64, participants completed all four booster sessions at home.

### 3. Hypotheses and Outcome Measures.

Hypothesis 1. Participants with MCI randomized to Games will show more improvement in cognitive outcomes as compared to Crosswords.

Primary outcome: ADAS-Cog 11 total score measured at baseline, 12 weeks, 52 weeks and 78 weeks.

Secondary outcome: Neuropsychological Testing Composite z-score measured at baseline, 12 weeks, 52 weeks and 78 weeks. Another secondary outcome, NCPT online cognitive performance test (measured at baseline and 78 weeks), was not analyzed because only 54 of 107 participants provided week 78 data due to software discontinuation.

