Hypothesis 1. MCI patients randomized to CCT will show better cognitive outcomes (primary: ADAS-Cog; secondary: Neuropsychological Testing Composite Score, exploratory: Neurocognitive Performance Test (NCPT)), by the end of the 18-month trial compared to patients randomized to active control. We will also compare the changes in the two randomized groups on the Neurocognitive Performance Test (NCPT), an exploratory outcome that is an online cognitive assessment battery.

Hypothesis 2. MCI patients randomized to CCT will show better functional outcomes (primary: UPSA, secondary: FAQ) by the end of the 18-month trial compared to patients randomized to active control.

Hypothesis 3. Brain pathology (smaller hippocampal volumes, lower odor identification scores on the UPSIT, ApoE e4 allele present) will moderate the relationship between treatment assignment and cognitive and functional outcomes.

Aim 2: To examine the effects of CCT on resting-state DMN connectivity as well as other networks modulated by CCT effects.

Hypothesis 1. MCI patients randomized to CCT will demonstrate greater change in an index of DMN functional connectivity compared to patients randomized to active control.

Hypothesis 2. Brain pathology (smaller hippocampal volumes, lower odor identification scores on the

UPSIT, ApoE e4 allele present) will moderate the relationship between change in the DMN and treatment assignment.

Aim 3: We will examine differences in rates of progression to dementia, and AD, in the two randomized treatment groups.

Hypothesis 1. The proportion converting to dementia will be lower in the CCT group compared to control.

Description of Subject Population

In this section, you are to describe each subject population of the study. The demographics of the population should reflect the gender and ethnic distribution of each population being studied. Enter each subject population's sample size, Gender, Racial, and Ethnic breakdown, and finally, describe each subject population.

Sample subject population:

Subject Population	Number of completers required to accomplish study aims	Projected number of subjects who will be enrolled to obtain required number of completers	Age range of subject population
Adults with Mild Cognitive Impairment (MCI)	50 at NYSPI; 50 at Duke University Medical Center	60 at NYSPI, 60 at Duke University Medical Center	55-95

Gender, Racial, and Ethnic Breakdown:

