Six feet of distance will be maintained between research staff and participants for all research assessments except for procedures where this is not possible, e.g., UPSIT.

While waiting in respective facility waiting area, staff will always maintain a distance of at least 6 feet from participants (subject and informant do not need to maintain a 6 foot distance from each other).

For neuropsychological tests: Research coordinator (tester) will place the materials on the clinic room desk and then guide the subject to complete the test, including verbal and written responses required for specific tests, from a distance greater than six feet whenever possible. If a clinic room with more than 6 feet of distance between tester and subject is not available, a conference room will be used.

Participants will be scheduled so that there is no overlap between participants in the waiting area.

Patients who are enrolled will be asked to come for the baseline visit, typically 1 week after the screening visit, and also following the MRI scan of the brain. Other measures include Contributing Features to MCI Form, ADAS-Cog 11, Online Neuropsychological Cognitive Performance Test, UPSA, Expectancy Scales (Participant and Informant), Stop/Bang Questionnaire, and the neuropsychological testing battery including the AVLT, WAIS-III Block Design subtest, Verbal Fluency, 15-item Boston Naming Task (BNT), Trail Making A and B, Visual Reproduction Test, and the WAIS-III Digit Symbol Substitution Test. The participant will also complete the 40-item UPSIT to assess baseline olfactory performance. The informant will complete the FAQ.

Protocol Summary Form

UPSIT specific: subjects will need to remove their masks during this smell test, but mask will be replaced by subject as soon as UPSIT is done. Subject will wear a face shield during testing administration, provided by staff. Study staff will give the subject the test to self-administer, and tester will guide the subject from minimum 6 feet away.

When neuropsych and UPSIT tests are complete, subject will be instructed to place all testing materials in a tray, which study staff will have placed on the desk prior to the visit session. At end of session, research coordinator will perform hand hygiene after interacting with materials handled by subjects. Non paper testing material will be disinfected with SaniCloth or Clorox wipes immediately after session.

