The GDS, FAQ, MMSE, ADAS-COG 11, User Engagement Scale, the neuropsychological testing battery, History of Game Use Questionnaire, and Digit Symbol Substitution Test will be completed. The participant will also complete the NCPT online cognitive test and cognitive training or control training booster session. The study physician or neuropsychologist will complete the Diagnosis Form. Research staff will also complete the Concomitant Medication Form.

Protocol Summary Form

20 -WEEK VISIT

This visit will be a follow up evaluation done over the phone. The FAQ will be completed by the informant. The participant will also complete cognitive training or control training booster session.

32-WEEK VISIT

All infection control guidelines and procedures stipulated at the top of the "Study Visit Procedures" section of the PSF (prior to description of screening visit) will be followed, as well as those infection control guidelines specific to neuropsychological testing, indicated in the Baseline/Week 0 visit description.

The GDS, MMSE, FAQ, Expectancy Scale (Participant and Informant), and UPSA will be completed. The study physician or neuropsychologist will complete the Diagnosis Form and Contributing Features to MCI Form. The participant will also complete cognitive training or control training booster session. Research staff will also complete the Concomitant Medication Form.

42-AT-HOME BOOSTER SESSION

During week 42, participants will complete a booster session (4 sessions) of at-home computerized cognitive training.

52 -WEEK VISIT

All infection control guidelines and procedures stipulated at the top of the "Study Visit Procedures" section of the PSF (prior to description of screening visit) will be followed, as well as those infection control guidelines specific to neuropsychological testing, indicated in the Baseline/Week 0 visit description.

The GDS, FAQ, ADAS-COG11, neuropsychological test battery, Digit Symbol Substitution Test, and MMSE will be completed. The participant will also complete cognitive training or control training booster session. Research staff will also complete the Concomitant Medication Form.

64-AT-HOME BOOSTER SESSION

During week 64, participants will complete a booster session (4 sessions) of at-home computerized cognitive training.

78 -WEEK VISIT

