All infection control guidelines and procedures stipulated at the top of the "Study Visit Procedures" (prior to description of screening visit) and Baseline/Week 0 sections of the PSF will be followed.

A MRI scan, GDS, CIRS-G, FAQ, MMSE, ADAS-Cog11, neuropsychological testing battery, Digit Symbol Substitution Test, Expectancy Scale (Participant & Informant), UPSA, UPSIT, History of Game Use Questionnaire, and User Engagement Scale, **Pittsburgh Sleep Quality Index (PSQI) and Epworth Sleepiness Scale (ESS)** will be completed. The study physician or neuropsychologist will complete the

Protocol Summary Form

Diagnosis Form and Contributing Features to MCI Form. The participant will also complete the NCPT online cognitive test and cognitive training or control training booster session.

Time Line. The sample (n=100) will be recruited over 3.5 years (includes 2 months start-up time to set up CCT platform and review MRI phantom scans). Treatment duration is 1.5 years. Total project duration is 5 years. Data entry/cleaning will be done throughout the project. Analyses and publications from baseline data will begin during the study and analyses of trial results will be done at the end of the trial.

Study duration: Total study duration may exceed 78 weeks for those participants encountering delays to in person assessments and/or procedures related to COVID-19 specific pauses to research protocol implementation. Any pause to research activity, specific to COVID-19, has, or may, be put into place as part of institutional risk reduction initiative(s). From a research perspective, this delay will be addressed by evaluating time in study as a covariate in statistical analyses of outcome measures, as appropriate.

Blindness of raters. The raters completing the outcome measures will be blind to which type of cognitive training (active or comparison) the patient is performing. Participants will be instructed not to discuss their online training with any tester or rater in order to maintain blindness.

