Other Measures: The Contributing Features to MCI Form is a form to be completed at weeks 0, 32, and 78 by the study physician or neuropsychologist. This form will indicate the contributing features to the patient's cognitive impairment. This measure will be used as a covariate; it is not a primary outcome measure. The History of Game Use Questionnaire is a questionnaire which assesses the past/present game use of the patient. This will be administered at screen, week 12, and week 78. This measure will be used as a covariate; it is not a primary outcome measure.

Medications: Medications will be listed and the Concomitant Medication Form (drug class list) will be completed at screen, 12, 32, 52, and 78. At weeks 12, 32, and 52 only medications changes to benzodiazepines, narcotics, and anticholinergics will be recorded. This measure will be used as a covariate; it is not a primary outcome measure.

Neurocognitive Performance Test. The Neurocognitive Performance Test (NCPT; developed by Lumos Labs, Inc.) is a brief, unsupervised, online battery of cognitive assessments used to measure functioning in five cognitive domains. The cognitive domains are memory (visuo-spatial working memory, short-term memory), processing speed (visual search, psychomotor speed), problem solving (logical reasoning, numerical calculation), attention (selective, divided), and flexibility (response inhibition, task-switching). The assessments ("subtests"), of which there are 10 total, are online adaptations of widely used neuropsychological tests whose shifting to computerized administration does not affect the test property. NCPT has minimal floor and ceiling effects, has shown good test-retest reliability in pilot analyses of tens of thousands of volunteers, and discriminated MCI from normal elderly in a registry study done at UCSF (unpublished data). It takes about 30 minutes, can be done at home, and new content is generated via algorithms to enable multiple repeated testing. In this study, users will be trained by sites to successfully complete a practice session before they do at-home testing. In NCPT scoring, subtest scores are percentile rank normalized within specific age bins, so that raw scores are transformed to a normal distribution with a mean of 100 and standard deviation of 15. The scaled subtest scores are then summed and the transformation is repeated to generate the aggregate overall score. NCPT change is an exploratory outcome.

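### The SAP leaves out the week-12 NCPT assessment that the protocol schedules, and leaves the whole outcome unanalysed on a week-78 count with no count or reason for week 12

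*SAP*

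**What the plan says.** **Protocol.** Three visits in Study Procedures include the NCPT:

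- Baseline/Week 0 Visit: "Other measures include Contributing Features to MCI Form, ADAS-Cog 11, Online Neuropsychological Cognitive Performance Test, UPSA".
- 12-Week Visit: "The participant will also complete the NCPT online cognitive test and cognitive training or control training booster session".
- 78-Week Visit, where it follows the physician's forms: "Diagnosis Form and Contributing Features to MCI Form. The participant will also complete the NCPT online cognitive test".

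It is not listed at weeks 20, 32 or 52. Specific Aims and Hypotheses (Aim 1, Hypothesis 1) commits to a between-arm analysis: "We will also compare the changes in the two randomized groups on the Neurocognitive Performance Test (NCPT), an exploratory outcome". The NCPT paragraph under Assessment Instruments repeats the rank: "NCPT change is an exploratory outcome".

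**SAP.** Section 3, Hypothesis 1, states: "Another secondary outcome, NCPT online cognitive performance test (measured at baseline and 78 weeks), was not analyzed because only 54 of 107 participants" had results at the last visit. The ground in full is that "only 54 of 107 participants provided week 78 data due to software discontinuation". The same section lists week 12 for both the ADAS-Cog 11 and the neuropsychological composite. Section 5 fits model (1) to change from baseline, tests the arms at each visit by contrasts, and relies on missing at random so that incomplete follow-up can be used.

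**The concern.** The two documents disagree on when the NCPT was scheduled and on its rank. The disagreement matters because of how the outcome was then handled. A shortfall at the last visit is used to leave out the whole outcome, although the protocol places another post-baseline assessment at the end of the 12-week training phase. Someone who reads only the SAP would not know that this assessment was planned.

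The Lay Summary asks whether an unsupervised web-based battery can detect training effects, and Aim 1 asks whether the arms differ on it. Under the SAP as written neither question is addressed, even partly. An unexplained gap in a scheduled outcome also leaves the report open to a question about selective reporting that would be cheap to answer.

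**Working it through.** **1. Schedules side by side.**

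| Source | Baseline | Week 12 | Week 78 | Rank |
|---|---|---|---|---|
| Protocol (visit descriptions; Aim 1; Assessment Instruments) | yes | yes | yes | exploratory |
| SAP section 3 | yes | not listed | yes | secondary |

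The difference is week 12, plus the rank.

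**2. What the SAP's count covers.** 54/107 = 50.5%, so 49.5% are missing, at week 78. The 54 is an observed count, and the documents give nothing from which to rebuild it. There is no corresponding figure for week 12.

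**3. Whether the planned model could use week 12.** Model (1) takes change scores at any set of post-baseline visits, treats visit as categorical and gives a Games-versus-Crosswords contrast at each. Weeks 12 and 78 fit it without modification.

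**4. Scale, as illustration only.** Inputs: 107 randomised 1:1 (SAP section 2); dropout uniform over time, reaching 20% at week 78 (SAP section 4). Assumptions: two-sided 5%, 80% power, equal arms, and week-12 NCPT loss equal to trial dropout.

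- Expected dropout at week 12: 0.20 × 12/78 = 3.1%.
- Expected number at week 12: 107 × (1 − 0.0308) = 103.7, about 104.
- Standard error of a difference in means, in SD units: 2/√N. This is 2/√54 = 0.272 and 2/√104 = 0.196.
- Detectable d, normal approximation: (1.960 + 0.842) × 2/√N. This is 0.76 for N = 54 and 0.55 for N = 104.
- Detectable d from the noncentral t distribution: 0.78 for N = 54 and 0.55 for N = 104.

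The 104 is a ceiling under this assumption, because a participant can remain in the trial and still not complete an at-home online test. If week-12 loss were already the full 20%, N would be 107 × 0.80 = 85.6, about 86, and the detectable d about 0.61 (noncentral t).

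**The case against.** The strongest reply is that a visit schedule states intent, whereas the SAP is retrospective: its introduction says that it describes analyses reported in the paper, and it writes of the NCPT in the past tense. Its two time points may record what was actually obtained. The discontinuation is not dated, so it may have cost some week-12 tests too. No document names a week-12 NCPT contrast, and Hypothesis 1 concerns outcomes by the end of 18 months. The SAP also discloses openly that the NCPT was not analysed.

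Most of this stands, and it rules out several stronger readings that a reader might infer:

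- **That the SAP's schedule is simply wrong, or that available data were ignored.** The documents do not show that week-12 data were collected, scored or retrievable.
- **That nearly all week-12 tests must have preceded the software loss.** Accrual closed in March 2020, so the last week-12 visits fell due around June 2020. But the discontinuation date is not given, and the protocol describes pandemic pauses and delays in that same period.
- **That week 12 is where the arms differ most in training intensity.** The protocol gives both arms the same session time and frequency; week 12 ends the intensive phase for both alike.
- **That week 12 should become the lead NCPT result.** That would be a choice of time point made after the fact, against hypotheses framed at 18 months.

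What the reply does not supply is any statement about week 12. If the data are absent, the SAP should say so; if they exist, the week-78 count does not explain leaving them out.

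**Conclusion.** The point holds as a gap between the documents with a modest analytic consequence. The protocol schedules an exploratory NCPT assessment at week 12 and plans a between-arm comparison of NCPT change. The SAP omits that visit, raises the outcome's rank to secondary, and leaves the outcome unanalysed on a week-78 figure alone. That a week-12 contrast belongs in the plan is an inference from three things together: the scheduled visit, the commitment in Aim 1 and the visit-by-visit contrasts of model (1).

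Whether anything was lost depends on a number that the documents do not give. The difference between a detectable d of about 0.55 and one of about 0.78 is the most that could be at stake under the stated dropout assumption; it shrinks as week-12 completion falls. The primary outcome and the sample size are not affected.

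**What to change.** In SAP section 3, reconcile the NCPT time points and its rank with the protocol, and state how many participants per arm have week-12 data.

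- **If week-12 data exist:** fit model (1) to NCPT change at the available visits. Report the week-12 Games-minus-Crosswords contrast with its 95% confidence interval and numbers per arm, labelled intermediate and exploratory and not presented as the lead NCPT result. Either confine the not-analysed statement to week 78, or report the week-78 contrast from the same model with the software loss stated beside it.
- **If week-12 data were not collected or were lost:** say so and give the reason.

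The cost is a few lines of text and, if there are data, one more run of a model already specified. The downside is one further exploratory comparison in a trial with no multiplicity adjustment, so the label must be explicit.
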